9 DATA AND SAFETY MONITORING PLAN

In the following section, there are references to "days", "calendar days", and "working days". References to "days" should be interpreted as calendar days. Working days include Monday through Friday with the exception of the following federal holidays (New Year's Day, Martin Luther King Jr.'s birthday, Washington's birthday, Memorial Day, Independence Day, Labor Day, Columbus Day, Veteran's Day, Thanksgiving Day, Christmas Day). Please note that the difference in reporting between the FDA required reporting (10 working days) and the UVA IRB requirement of 10 calendar days for Unanticipated Adverse Device Effects (UADEs)(for device studies only). For reporting to the IRB, follow the more conservative guideline (e.g. calendar days).

9.1 Adverse Events and Serious Adverse Events

9.1.1 Definition of Adverse Events (AE)

Pre-Operative Window of Adjuvant Endocrine Therapy to Inform Radiation Therapy Decisions in Older Women with Early-Stage Breast Cancer

Version Date: 21 February 2023

Adverse event means any untoward medical occurrence associated with the use of an intervention in humans, whether or not considered intervention-related (21 CFR 312.32 (a)).

9.1.2 Definition of Serious Adverse Events (SAE)

An adverse event (AE) or suspected adverse reaction is considered "serious" if, in the view of either the investigator or sponsor, it results in any of the following outcomes:

- death,
- a life-threatening adverse event,
- inpatient hospitalization or prolongation of existing hospitalization,
- a persistent or significant incapacity or substantial disruption of the ability to conduct normal life functions, or
- a congenital anomaly/birth defect.

Important medical events that may not result in death, be life-threatening, or require hospitalization may be considered serious when, based upon appropriate medical judgment, they may jeopardize the participant and may require medical or surgical intervention to prevent one of the outcomes listed in this definition. Examples of such medical events include allergic bronchospasm requiring intensive treatment in an emergency room or at home, blood dyscrasias or convulsions that do not result in inpatient hospitalization, or the development of drug dependency or drug abuse.

Note: A planned medical or surgical procedure is not, in itself, an SAE

9.1.3 Classification of an Adverse Event

9.1.3.1 Severity of Event

The NCI Common Terminology Criteria for Adverse Events (CTCAE) version 5 will be used for the characterization and grading of adverse events.

9.1.3.2 Relationship to Study Intervention

All adverse events (AEs) must have their relationship to study intervention assessed by the clinician who examines and evaluates the participant based on temporal relationship and his/her clinical judgment. The degree of certainty about causality will be graded using the categories below. In a clinical trial, the study product must always be suspect.

- **Definitely Related** – There is clear evidence to suggest a causal relationship, and other possible contributing factors can be ruled out. The clinical event, including an abnormal laboratory test result, occurs in a plausible time relationship to study intervention administration and cannot be explained by concurrent disease or other drugs or chemicals. The response to withdrawal of the study intervention (dechallenge) should be clinically plausible. The event must be pharmacologically or phenomenologically definitive, with use of a satisfactory rechallenge procedure if necessary.
- **Probably Related** – There is evidence to suggest a causal relationship, and the influence of other factors is unlikely. The clinical event, including an abnormal laboratory test result, occurs within a reasonable time after administration of the study intervention, is unlikely

Pre-Operative Window of Adjuvant Endocrine Therapy to Inform Radiation Therapy Decisions in Older Women with Early-Stage Breast Cancer

Version Date: 21 February 2023

to be attributed to concurrent disease or other drugs or chemicals, and follows a clinically reasonable response on withdrawal (dechallenge). Rechallenge information is not required to fulfill this definition.

- **Possibly Related** – There is some evidence to suggest a causal relationship (e.g., the event occurred within a reasonable time after administration of the trial medication). However, other factors may have contributed to the event (e.g., the participant's clinical condition, other concomitant events). Although an AE may rate only as "possibly related" soon after discovery, it can be flagged as requiring more information and later be upgraded to "probably related" or "definitely related", as appropriate.
- **Unlikely to be related** – A clinical event, including an abnormal laboratory test result, whose temporal relationship to study intervention administration makes a causal relationship improbable (e.g., the event did not occur within a reasonable time after administration of the study intervention) and in which other drugs or chemicals or underlying disease provides plausible explanations (e.g., the participant's clinical condition, other concomitant treatments).
- **Not Related** – The AE is completely independent of study intervention administration, and/or evidence exists that the event is definitely related to another etiology. There must be an alternative, definitive etiology documented by the clinician.

9.1.3.3 Expectedness

Pre-operative Endocrine Therapy

The Principal Investigator will be responsible for determining whether an adverse event (AE) is expected or unexpected. An AE will be considered unexpected if the nature, severity, or frequency of the event is not consistent with the risk information previously described for the study intervention in the prescribing information for each drug.

9.1.4 Time Period and Frequency for Event Assessment and Follow-Up

The occurrence of an adverse event (AE) or serious adverse event (SAE) may come to the attention of study personnel during study visits and interviews of a study participant presenting for medical care, or upon review by a study monitor.

All AEs including local and systemic reactions not meeting the criteria for SAEs will be captured on the appropriate case report form (CRF). Information to be collected includes event description, time of onset, clinician's assessment of severity, relationship to study product (assessed only by those with the training and authority to make a diagnosis), and time of resolution/stabilization of the event. All AEs occurring while on study must be documented appropriately regardless of relationship. All AEs will be followed to adequate resolution.

Any medical condition (including a laboratory abnormality) that is present at the time that the participant is screened will be considered as baseline and not reported as an AE. However, if the

Pre-Operative Window of Adjuvant Endocrine Therapy to Inform Radiation Therapy Decisions in Older Women with Early-Stage Breast Cancer

Version Date: 21 February 2023

study participant's condition deteriorates at any time during the study, it will be recorded as an AE.

Changes in the severity of an AE will be documented to allow an assessment of the duration of the event at each level of severity to be performed. AEs characterized as intermittent require documentation of onset and duration of each episode.

A member of the study team will record all reportable events with start dates occurring any time after informed consent is obtained until 30 days (for non-serious AEs) or anytime (for SAEs considered related to the study intervention) after the last day of neo-adjuvant endocrine therapy, or until another therapy is started. At each study visit, the investigator will inquire about the occurrence of AE/SAEs since the last visit. Events will be followed for outcome information until resolution or stabilization.

9.1.5 Adverse Event Reporting

AEs must be recorded into the University of Virginia Cancer Center (UVA Cancer Center) database per guidelines in [Table 1](#).

Table 1: Recording Guidelines for UVA

Cancer Center Database

Medium Risk Studies									
Reporting requirements for AEs that occur within 30 days of the last dose of protocol specified treatment									
	Grade 1	Grade 2		Grade 3				Grade 4 & 5	
	Expected and unexpected	Expected	Unexpected	Expected		Unexpected		Expected	Unexpected
Unrelated	Not required	Not required	Not required	OnCore 30 days	OnCore 15 days	OnCore 30 days	OnCore 15 days	OnCore 15 days	OnCore 15 days
Possible	OnCore 30 days	OnCore 30 days	OnCore 15 days	OnCore 30 days	OnCore 15 days	OnCore 15 days	OnCore 15 days	OnCore 15 days	OnCore (24-hrs)* 7 days
Probable									
Definite									

*Enter into Cancer Center database within 24 hours if unexpected and definitely related to protocol specified treatment

Hospitalization defined as an inpatient hospital stay or prolongation of a hospital stay equal to or greater than 24 hours

9.1.6 Serious Adverse Event Reporting

Pre-Operative Window of Adjuvant Endocrine Therapy to Inform Radiation Therapy Decisions in
Older Women with Early-Stage Breast Cancer

Version Date: 21 February 2023

The study clinician will report to the sponsor any serious adverse event, whether or not considered study intervention related, including those listed in the protocol or drug labels, and must include an assessment of whether there is a reasonable possibility that the study intervention caused the event. Study endpoints that are serious adverse events (e.g., all-cause mortality) must be reported in accordance with the protocol unless there is evidence suggesting a causal relationship between the drug and the event (e.g., death from anaphylaxis). In that case, the investigator must immediately report the event to the sponsor.

All serious adverse events (SAEs) will be followed until satisfactory resolution or until the site investigator deems the event to be chronic or the participant is stable. Other supporting documentation of the event may be requested by the UVA Multisite Clinical Research Office (UVA MCRO/Sponsor) and should be provided as soon as possible

Site Reporting Requirements

- Report to the UVA MCRO within 24 hours from the time the study team received knowledge of the event according to UVA MCRO requirements.
- Report to your IRB in accordance with your IRB guidelines.

Multi-Site Principal Investigator / UVA MCRO Reporting Requirements

- The Sponsor (or the UVA MCRO on behalf of the sponsor) is responsible for notifying the UVA IRB-HSR of any event resulting in death that is deemed DEFINITELY related to (caused by) study within 24 hours from the time the study team received knowledge of the event. Report using IRB Online and by telephone.
- The Sponsor (or the UVA MCRO on behalf of the sponsor) is responsible for notifying the UVA IRB-HSR of any serious, unexpected, related adverse event within 7 calendar days from the time the study team receives knowledge of the event. Timeline includes submission of signed hardcopy of AE form. Report using IRB online.

9.2 Reporting Events to Participants

If there is any new information relevant to the participant's willingness to continue to participate in the study, such as if there are new risks of the study treatment identified that were not included on the consent form that the participant signed, the study team will contact the participant to discuss this information. If the participant is still receiving study treatment, the study team will present the participant with an updated consent and confirm that he or she wants to continue receiving study treatment. The Principal Investigator will determine whether new risks are applicable to participants who are in follow-up, whether participants need to be notified, and whether re-consenting is required.

9.3 Unanticipated Problems

9.3.1 Definition of Unanticipated Problems (UP)

Pre-Operative Window of Adjuvant Endocrine Therapy to Inform Radiation Therapy Decisions in Older Women with Early-Stage Breast Cancer

Version Date: 21 February 2023

The Office for Human Research Protections (OHRP) considers unanticipated problems (UPs)(may include a data breach) involving risks to participants or others to include, in general, any incident, experience, or outcome that meets all of the following criteria:

- Unexpected in terms of nature, severity, or frequency given (a) the research procedures that are described in the protocol-related documents, such as the Institutional Review Board (IRB)-approved research protocol and informed consent document; and (b) the characteristics of the participant population being studied;
- Related or possibly related to participation in the research (“possibly related” means there is a reasonable possibility that the incident, experience, or outcome may have been caused by the procedures involved in the research); and
- Suggests that the research places participants or others at a greater risk of harm (including physical, psychological, economic, or social harm) than was previously known or recognized.

9.3.2 Unanticipated Problem Reporting

To satisfy the requirement for prompt reporting, UPs will be reported using the following timeline:

Site Reporting Requirements

- UPs that are SAEs will be reported in accordance with the guidelines for SAE reporting.
- UPs that are not adverse events, protocol deviations or data breaches (see [section 9.4.2](#) for reporting for data breaches)
 - Report to the UVA MCRO within 2 calendar days from the time the study team receives knowledge of the event.
 - Report to your IRB of record in accordance with your IRB guidelines.

Multi-Site Principal Investigator/UVA MCRO/Study Team Reporting Requirements

- Report UPs that are not adverse events or protocol deviations to the UVA IRB-HSR within 7 calendar days from the time the study team receives knowledge of the event. Report using the Unanticipated Problem Report form.
- All UPs will be reported to appropriate institutional officials (as required by an institution's written reporting procedures), the supporting agency head (or designee), and the Office for Human Research Protections (OHRP) in accordance with institutional policies.

9.3.3 Reporting Unanticipated Problems to Participants

If during the course of the study there is an unanticipated problem that affects current or past participants, affected participants will be contacted if needed.

9.4 Data Breach

9.4.1 Definition of Data Breach

An unauthorized acquisition, access, or use of protected health information (PHI) that compromises the security or privacy of such information.

9.4.2 Reporting a Data Breach

Site Reporting Requirements

- Report to the UVA MCRO within 24 hours from the time the study team receives knowledge of the event.
- Report to your IRB of record in accordance with your IRB guidelines.

Multi-Site Principal Investigator (or UVA MCRO on behalf of the sponsor) Reporting Requirements

- Report to the UVA Corporate Compliance and Privacy Office as soon as possible and no later than 24 hours from the time the incident is identified. Report by telephone.
- Report to ITC if the breach involves electronic data. Report as soon as possible and no later than 24 hours from the time the incident is identified. Refer to the following for details: <http://security.virginia.edu/report-information-security-incident>.
- Report to UVA police if the breach includes such things as stolen computers. Report by telephone.

9.5 Protocol Deviation

9.5.1 Definition of Protocol Deviation

A protocol deviation is defined as any change, deviation, or departure from the study design or procedures of a research project that is NOT approved by the institution's IRB prior to its initiation or implementation, OR deviation from standard operating procedures, Good Clinical Practices (GCPs), federal, state or local regulations. Protocol violations may or may not be under the control of the study team or site staff. These protocol violations may be major or minor violations.

9.5.2 Reporting of a Protocol Deviation

It is the responsibility of the site investigator to use continuous vigilance to identify and report deviations. All deviations must be addressed in study source documents.

Site Reporting Requirements

- Report major deviations to the UVA MCRO within 4 calendar days from the time the study team receives knowledge of the event. Consult the MCRO for instructions on recording minor deviations.
- Report to your IRB of record in accordance with your IRB guidelines.
(For sites that use the UVA IRB-HSR as the IRB of record, the UVA MCRO will report to the UVA IRB-HSR as required—see sponsor reporting requirements)

Multi-Site Principal Investigator Reporting Requirements

Pre-Operative Window of Adjuvant Endocrine Therapy to Inform Radiation Therapy Decisions in Older Women with Early-Stage Breast Cancer

Version Date: 21 February 2023

- Report to the UVA IRB-HSR major deviations within 7 calendar days from the time the study team received knowledge of the event. Report using the Protocol Deviation and Protocol Exception Reporting Form.

For minor deviations, please reference the UVA IRB-HSR website for tips for recording minor deviations

9.6 Participant Withdrawals/Dropouts Prior to Study Completion

Participants who withdraw consent and those dropping out of the study secondary to an AE will be reported to the IRB yearly on the IRB continuation form.

10 STATISTICAL CONSIDERATIONS

10.1 Study Design Overview

This is a prospective multicenter study to obtain preliminary information on whether pre-treatment with endocrine therapy changes preference for adjuvant radiation treatment as considered by the participant or the surgical oncologist. In addition, we aim to capture a range of patient reported outcomes over time to explore the possibility that these measures will be useful predictors of adherence to post-operative endocrine therapy.

10.2 Endpoints, Statistical Hypotheses and Estimation

Assessment of the primary study objectives will be based upon answers to the radiation preference question for study participants and surgical oncologists separately. Change in preference is measured as a binary variable (yes/no) with a coding of 'yes' if answers between the pre-op and on-study (baseline) response differ (no to yes; or yes to no). No difference in response is coded as 'no'.

Hypothesis test 1: To determine if pre-treatment with endocrine therapy changes participant preference for adjuvant radiation treatment in the participant study population by at least 10% with a one-sided binomial test.

Hypothesis test 2: To determine if pre-treatment with endocrine therapy changes surgical oncologist preference for participant specific adjuvant radiation treatment in the participant study population by at least 10% with a one-sided binomial test.

Estimation: To estimate the association of pre-treatment PRO measures on the probability of long-term adjuvant endocrine therapy adherence.

10.3 Sample Size Determination

Sample size estimation is based upon accruing a sufficient number of participants to assess the primary objective separately for participants and surgical oncologist responses with an overall one-sided 10% type I error rate (5% for each individual test). Accrual of 70 evaluable participants provides 90% power to test for a change in adjuvant radiation treatment preference between the pre-op visit and on-study in the participant study population from a null difference of 5% to an alternative of at least 15% with a target one-sided 5% level binomial test (by exact enumeration). Accrual of 70 evaluable participants also provides 90% power to independently test for a change

Pre-Operative Window of Adjuvant Endocrine Therapy to Inform Radiation Therapy Decisions in Older Women with Early-Stage Breast Cancer

Version Date: 21 February 2023

in adjuvant radiation treatment preference of the surgical oncologist between the pre-op visit and on-study in the participant study population from a null difference of 5% to an alternative of at least 15% with a one-sided 5% level binomial test. For fixed target size and power, the detectable difference increases from 10% to 15% when the assumed null varies within the expected range of 5% to 20%.

This is a pilot study to obtain preliminary data to estimate which if any PRO measures are associated with adherence to post-operative endocrine therapy. With n=70, a logistic regression of the dependent variable of adherence or not to endocrine therapy by year 2 on a continuous PRO measure score achieves 80% power at a 5% significance level to detect an odds ratio of 2 when the probability of adherence is 25%. These error rate estimates assume no adjustment for multiple comparisons among the different PRO.

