10.4 Accrual

Maximum target sample size is estimated at 83 eligible participants which adjusts for a 15% lost to follow-up/dropout rate. In 2018 and 2017, 70 and 78 patients, respectively, met the basic inclusion criteria at UVA. Assuming 60% of future patients will agree to enroll in the study, target accrual to the study should be achieved in less than two years.

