10.5.2 Analyses

Primary analyses will not adjust for center. Summary measures will be described overall and by center. Demographics and baseline characteristics will be described for all study participants. Characteristics to be examined include: race/ethnicity, age, performance status, stage, ER, PR and HER-2 status, histologic subtype, tumor size date of diagnosis.

Adverse events will be coded based upon the NCI CTCAE v5.0. Safety will be reported by frequency and severity of adverse events.

The primary analysis will be based upon responses from a) study participants and b) surgical oncologists to the radiation questions, separately, without adjustment for center. For each response group, the proportion of responses that differ from the pre-op visit compared to the on-study (baseline) response (yes to no; or no to yes) will be calculated along with 95% confidence intervals. For each group, we will test that pre-ET resulted in a change in preference for adjuvant

Pre-Operative Window of Adjuvant Endocrine Therapy to Inform Radiation Therapy Decisions in Older Women with Early-Stage Breast Cancer

Version Date: 21 February 2023

radiation therapy in more than 10% of participants compared to no change with a one-sided 5% level exact binomial test.

Graphical methods will be used to display the PRO outcomes over time. On the most basic level, logistic regression models with adherence to post-op endocrine therapy at 2 years as the dependent outcome and the range of PRO measurement as independent factors will be used to obtain initial estimates of the predictive value of the protocol defined PRO to determine adherence. Other exploratory repeated measures models will be explored to determine if changes over time are also associated with determination of non-adherence. Exploratory analyses could include the assessment of PRO for quality adjusted life years or healthy-year equivalents. In all exploratory models, individual or simultaneous associations will be deemed promising for factors with $p < 0.1$.

The secondary analysis related to the radiation oncologist's preference will be based upon the subset of pre and post pre-ET responses from for the consulting radiation oncologist. The proportion of responses that differ from the pre-op visit compared to the on-study (baseline) response by at least one point (in either direction) will be calculated along with a 95% confidence interval.

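### At n=70 the one-sided 5% exact test has 84% power, not the stated 90%, and Sections 10.2 and 10.5.2 do not state the 5% null used in 10.3

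*Combined protocol and SAP*

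**What the plan says.** Section 10.3 sets the design for two primary tests, one on participants' radiation preference and one on the surgical oncologist's:

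- **Error rate:** "overall one-sided 10% type I error rate (5% for each individual test").
- **Power:** "Accrual of 70 evaluable participants provides 90% power to test for a change in adjuvant radiation treatment preference".
- **Participant test:** "from a null difference of 5% to an alternative of at least 15% with a target one-sided 5% level binomial test (by exact enumeration").
- **Surgical oncologist test:** "null difference of 5% to an alternative of at least 15% with a one-sided 5% level binomial test", again with 90% power at 70 evaluable. The qualifier *target* does not appear here.
- **Range of nulls:** "For fixed target size and power, the detectable difference increases from 10% to 15" per cent as the assumed null runs from 5% to 20%.

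Section 10.4 sets the enrolment cap: "Maximum target sample size is estimated at 83 eligible participants which adjusts for a 15% lost to follow-up/dropout rate".

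The other two sections word the hypothesis differently. Section 10.2 asks whether pre-ET "changes participant preference for adjuvant radiation treatment in the participant study population by at least 10% with a one-sided binomial test", with the same form for the surgical oncologist. Section 10.5.2 tests for change in "radiation therapy in more than 10% of participants compared to no change with a one-sided 5% level exact binomial test". Neither gives a 5% null. No section gives a rejection cut-off or an attained size.

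**The concern.** There are two problems, and the second is the more serious.

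First, the count of changed preferences is an integer, so an exact test at n=70 offers only a few attainable sizes. The 90% power and the 5% level in 10.3 need a cut-off that delivers both, and none exists. Seven changes out of 70 would have to count as a success for the stated power to hold, yet 7/70 gives p=0.060 in the test that 10.5.2 prescribes.

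Second, the power is computed against a 5% null, while the analysis section names 10%. An analyst following 10.3 and one following 10.5.2 could reach opposite conclusions on both primary hypotheses from the same data. The results on which they would disagree include those expected at the design alternative (0.15 × 70 = 10.5 changes).

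**Working it through.** **Inputs.** n=70 evaluable, null 5%, alternative 15%, one-sided 5% per test and 10% overall (10.3); 10% threshold (10.2, 10.5.2); 15% dropout and cap of 83 (10.4). X is the number of changed preferences, X ~ Binomial(n, p). For a cut-off c, size = P(X ≥ c | null rate) and power = P(X ≥ c | true rate).

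**Step 1: tail probabilities at n=70.**

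| Reject at | P at 5% | P at 10% | P at 15% |
|---|---|---|---|
| ≥7 | 0.0604 | 0.558 | 0.9162 |
| ≥8 | 0.0234 | 0.401 | 0.8430 |
| ≥9 | 0.0080 | 0.264 | 0.7412 |
| ≥10 | 0.0025 | 0.159 | 0.6174 |
| ≥11 | 0.0007 | 0.087 | 0.4842 |
| ≥12 | 0.0002 | 0.0441 | 0.3560 |

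**Step 2: where the plan's figure comes from.** Choosing the cut-off whose size is nearest to 5%, even if above it, gives c=7, with power 91.6% and size 6.0%. With that cut-off, 90% power is reached at a true rate of 14.56%, which is 9.6 points above the null. For a 20% null the same convention gives c=20 (size 5.45%) and 90% power at 35.1%, which is 15.1 points above. So the 90% and the 10-to-15-point range both follow from this convention.

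**Step 3: the level-5% test.** Holding the size at or below 5% gives c=8, with size 2.34% and power 84.3% (type II error 15.7%). Power of 90% needs a true rate of 16.2%, or 11.2 points above the null. For a 20% null, c=21 (size 3.03%) and 90% power needs 36.6%, or 16.6 points above.

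**Step 4: overall error for two tests, each with a 5% null.**
- Cut-off ≥7: 2 × 0.0604 = 12.1% by sum; 1 − (1 − 0.0604)² = 11.7% if independent.
- Cut-off ≥8: 4.7% by sum; 4.6% if independent.

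**Step 5: 10% as the null.** The level-5% cut-off is ≥12 (size 4.41%). Power is 35.6% at a true rate of 15% and 76.8% at 20%; 90% needs 22.8%. The cut-offs for the two nulls are 8 and 12, so results of 8, 9, 10 or 11 (11.4% to 15.7%) reject a 5% null but not a 10% null. At a true rate of 15% the chance of landing there is 0.8430 − 0.3560 = 48.7%.

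**Step 6: dependence on the evaluable number** (5% null, level-5% test, true rate 15%).

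| Evaluable | Cut-off | Size | Power |
|---|---|---|---|
| 66 | 7 | 4.6% | 88.4% |
| 67 | 7 | 5.0% | 89.3% |
| 68 | 8 | 2.0% | 81.9% |
| 70 | 8 | 2.3% | 84.3% |
| 76 | 8 | 3.6% | 89.99% |
| 77 | 8 | 3.8% | 90.7% |
| 81 | 8 | 5.0% | 93.3% |
| 82 | 9 | 2.1% | 88.4% |
| 83 | 9 | 2.3% | 89.2% |

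The dropout allowance itself is right: 70/0.85 = 82.4, rounded up to 83.

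**The case against.** The best defence is that 10.3 contains no slip of arithmetic. It calls the participant test's level a target and later speaks of a fixed target size after describing both tests. Read as the nearest attainable size, that convention reproduces every primary-test figure. This stands as an explanation of where the 90% comes from. It does not make the plan consistent, because 10.5.2 prescribes a 5% level exact test without that latitude, and the 6.0% and 12% attained sizes are not disclosed and exceed the 5% and 10% stated.

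It is also fair that the written analysis would not inflate type I error. No section sets a cut-off of 7, so under 10.5.2 a result of 7/70 would simply fail. The practical effect of the first problem is therefore about six points of overstated power, which alone is minor in a pilot that also reports 95% confidence intervals. The 84.3% is specific to 70 evaluable: power is 88% to 89% at 66 or 67 and 89% at 83.

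Finally, the 10% in 10.2 may mean the 10-point difference between 5% and 15%. That reading is open for 10.2. It is hard to sustain for 10.5.2, which speaks of a proportion of participants above 10% and then adds a comparison with no change, a further possible reading.

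**Conclusion.** The concern holds. At the stated n=70 and 5% null, a one-sided exact test held to 5% has 84.3% power at 15%, not 90%. The cut-off that exceeds 90% power has a size of 6.0% per test. More important, the three sections do not state one null: 10.3 uses 5%, 10.5.2 reads as 10%, and 10.2 is ambiguous. Results of 8 to 11 changes out of 70 succeed or fail accordingly, and under a 10% null the power at 15% is 36%.

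These figures assume exactly 70 evaluable participants for each test, a non-randomised exact binomial test, and independent responses. The power figures change with the evaluable number, as shown, but the conflict over the null does not depend on it.

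**What to change.** Use one null in 10.2, 10.3 and 10.5.2, and state the decision rule before the data are analysed.

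If the 5% null is intended, 10.2 and 10.5.2 could read: *H0: change rate ≤5% versus H1: >5%, one-sided exact binomial test at level ≤5%, powered at a change rate of 15% (a 10-point increase).* Section 10.3 could read: *With 70 evaluable participants the test rejects at 8 or more changes (attained size 2.3%), with 84% power at 15% and 90% power at 16.2%. The detectable difference is about 11 to 17 points for nulls of 5% to 20%. The cut-off will be recomputed for the actual evaluable number.* The same text should apply to the surgical oncologist test.

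This costs wording only if 84% power is accepted. Within the cap of 83, power of 90% or more needs 77 to 81 evaluable, which means dropout of 2% to 7% (1 − 81/83 to 1 − 77/83) instead of 15%. Keeping 15% dropout and aiming for 77 evaluable means enrolling 91 (77/0.85 = 90.6).

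If a 10% null is intended, 10.3 must be redone. Power of 90% would first be reached at 109 evaluable for a true rate of 20%, or 368 for 15%, both beyond the cap.
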